7.6 Study Drug Accountability

Vaccine accountability will be maintained by the study pharmacist.

7.7 Study Drug Handling and Disposal

Vaccine handling and disposal will be managed by the study pharmacist.

7.8 Contraindications and Warnings

7.8.1 Prohibited Medications

Treatment with the following medications during the study is prohibited:

- metformin
- aspirin > 160 mg/day
- chronic daily NSAIDS

- immunosuppressants including calcineurin inhibitors, corticosteroids, or biological or cytotoxic immunosuppressants (e.g. imuran, methotrexate, cyclosporine, etanercept, infliximab)
- antibiotics within 14 days of immunizations
- additional live vaccinations within 60 days of BCG immunizations

7.8.2 **Warnings**

BCG contains live, attenuated mycobacteria, and carries risk for adverse consequences particularly in immunocompromised individuals for whom the attenuated strain could become pathogenic as described below (section 9.1, BCG vaccine risks).

8 BIOSTATISTICAL ANALYSIS

8.1 Statistical methods

This is a single-site, open-label pilot clinical trial in which twelve older adult volunteers with normal cognition or MCI will be recruited for BCG vaccination with the intent of generating preliminary descriptive data on IIR and neurobiological biomarker effects and evaluate tolerability, safety and study feasibility. No sample size calculations are performed as no prespecified comparisons are planned. Statistical analyses will describe baseline characteristics of the sample and change in biomarkers, safety and clinical measures, with pre-post paired t-tests or non-parametric equivalents (Wilcoxon sign-rank) used to evaluate within subject change. All outcomes in this pilot study are considered exploratory and no claims are attached to them, thus multiple comparison correction is not applied. A P value <0.05 will be considered significant. Findings will be used to inform the design of subsequent placebo-controlled trials of BCG vaccination for prevention and/or disease modification of Alzheimer's disease and related disorders.

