3 STUDY DESIGN

3.1 Overall Study Design and Plan

This single-site, open-label clinical trial will investigate the immune and neurobiological biomarker effects of BCG vaccination in healthy older adults and older adults with mild cognitive impairment (MCI), and gather data on tolerability, safety and study feasibility. Twenty participants (approx. n=10 cognitively normal, n=10 mild cognitive impairment) will receive two intradermal BCG vaccinations spaced 4 weeks apart and will be evaluated 12 weeks after the initial immunization. Cerebrospinal fluid (CSF) and blood will be collected at Screening (blood only), Baseline, Week 4 (blood only), and Week 12 for to assess safety, IIR and AD biomarkers.

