4.2 Recruitment

Up to twenty-six subjects will be screened and enrolled in the study, and after screening we expect twenty subjects to complete the study.

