6.2.1.3 Screen Failures

Any subject who signs consent will be considered enrolled in the study. If a subject fails screening, *at a minimum*, the following information should be captured and entered into the Electronic Data System (EDC).

- Inclusion/Exclusion Criteria
- Demographics
- Reason for screen failure

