7.4 Study Drug Preparation

The BCG vaccine is supplied as a 10-dose ampoule. For reconstitution, 1.0 ml of sterile saline is added to the 10-dose ampoule. Each 0.1ml dose is drawn by syringe from the ampoule following reconstitution and administered intradermally. Once reconstituted, the pharmacy provides the study clinic with the pre-filled syringe in a covered surgical tray to prevent light exposure. If the prepared syringe cannot be immediately administered, it will be temporarily stored at 4°C until administration (< 1 hour from reconstitution).

Each ampoule may be used for a maximum of two study participants in this pilot study of 12 participants. In this case, the ampoule will be reconstituted, and the syringes drawn at the same time. As above, the prepared syringes will be covered and stored at 4°C until administration within 1 hour of reconstitution. The remaining unused volume in the ampoule will not be used for additional patients in this pilot trial.

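### The planned sample size contradicts itself: 12 participants in sections 8.1 and 7.4, 20 in sections 3.1 and 4.2

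*Combined protocol and SAP*

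**What the plan says.** The document gives two planned sizes, each in two sections.

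- Section 8.1 (Statistical methods) describes a single-site, open-label pilot "in which twelve older adult volunteers with normal cognition or MCI will be recruited for BCG vaccination". It gives no split between the cognitive groups.
- Section 7.4 (Study Drug Preparation) repeats that number: "Each ampoule may be used for a maximum of two study participants in this pilot study of 12 participants".
- Section 3.1 (Overall Study Design and Plan) states: "Twenty participants (approx. n=10 cognitively normal, n=10 mild cognitive impairment) will receive two intradermal BCG vaccinations spaced 4 weeks apart". The same sentence goes on to say that they will be evaluated 12 weeks after the first vaccination.
- Section 4.2 (Recruitment) states: "Up to twenty-six subjects will be screened and enrolled in the study, and after screening we expect twenty subjects to complete the study".

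Two further statements bear on how these are read. Section 6.2.1.3 (Screen Failures) defines enrolment by consent: "Any subject who signs consent will be considered enrolled in the study". Section 8.1 gives no derivation for its number: "No sample size calculations are performed as no prespecified comparisons are planned".

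**The concern.** The number of participants is a basic design fact, and the section that describes the analysis disagrees with the section that describes the design. With no power calculation, effect size or standard deviation in the document, a reader cannot work out which number was intended.

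Three things depend on it. First, the precision of the pre-post changes, which are meant to inform later placebo-controlled trials. Second, how much the study can say about safety, which section 3.2 lists as a secondary objective. Third, the size of the cognitive groups: section 3.3.1 allows biomarker comparisons between groups, section 3.1 plans about 10 in each, and that split cannot be carried over to a total of 12.

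As written, stopping at 12 or continuing to 20 would each agree with two sections and contradict the other two. A shortfall or an overrun could not be judged against the plan.

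**Working it through.** **Can either number be reproduced?** No. The document gives no power, effect size or SD, so neither 12 nor 20 can be derived. The check is a direct comparison of the stated counts, followed by what each would mean.

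**Comparing the counts**

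- Section 3.1 agrees with itself: 10 + 10 = 20.
- Sections 3.1 and 4.2 agree on 20; sections 8.1 and 7.4 agree on 12.
- The gap is 20 − 12 = 8 participants, or 8/20 = 40% of the larger figure.
- Screen failure or dropout does not explain it. Sections 8.1 and 3.1 both count people to be vaccinated, and 20 completers cannot come from 12 recruits.
- The ceiling of 26 in section 4.2 is not part of the conflict. Enrolment starts at consent, so 26 consented and 20 completing are compatible. They leave 26 − 20 = 6 (6/26 = 23%) for screen failures and losses.

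**Precision of a mean paired change.** The 95% confidence interval half-width, in SDs of the change, is t(0.975, n−1)/√n. Complete data are assumed.

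- n = 12: 2.201/3.464 = 0.635
- n = 20: 2.093/4.472 = 0.468
- Ratio: 0.635/0.468 = 1.36, so the interval is 36% wider at 12.

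If about 15% had no Day 84 sample (an assumption; the document gives no rate), 12 becomes about 10 and 20 becomes 17.

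- n = 10: 2.262/3.162 = 0.715
- n = 17: 2.120/4.123 = 0.514

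**Safety.** With zero events among n vaccinated participants, the one-sided 95% upper limit for the event rate is 1 − 0.05^(1/n).

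- n = 12: 1 − 0.05^(1/12) = 0.221, or 22.1%
- n = 20: 1 − 0.05^(1/20) = 0.139, or 13.9%

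**Vaccine supply.** Each participant has two vaccinations, and section 7.4 allows at most two participants per ampoule. The minimum number of ampoules is therefore 2n/2 = n.

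- n = 12: 24/2 = 12 ampoules
- n = 20: 40/2 = 20 ampoules

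These minimums assume that participants can be paired perfectly at both vaccination visits.

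**The case against.** The best counter-argument is that this is an editorial leftover with no analytic consequence. Section 8.1 says no sample size calculation was made and treats every outcome as exploratory. No confirmatory test or allocation of alpha depends on the planned number. The systemic-infection stopping rule in section 5.6 uses subjects actually enrolled, so it can be applied whichever number was planned. That is correct, and it is why the effect is described here as one on precision and clarity, with no stated calculation overturned. It does not remove the conflict. The smaller number appears in two separate sections, once as a word and once as a numeral, so a single slip or a PDF-reading error is an unlikely explanation, and nothing in the text shows which number is current.

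Some narrower points stand and limit the illustrations.

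- Section 3.1 has its twenty both vaccinated and evaluated at Week 12, which fits the twenty completers in section 4.2. Whether 20 counts those vaccinated or those completing is a minor clarification.
- If 20 is already the number completing, taking off a further 15% applies only to completers who lack a Day 84 sample. More than 20 might also then be vaccinated, and the zero-event limit would be a little below 13.9%.
- The handling rules in section 7.4 do not depend on the total, and no supply quantity is stated. The ampoule counts show scale and contradict nothing in the text.
- Section 8.1 plans description and paired tests. Adding a statement of interval precision would be a preference.

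**Conclusion.** The concern holds. Two sections plan for 12 participants and two plan for 20. All four are current text, and no reading of them together makes the figures agree. The difference is 8 participants. It changes the 95% half-width for a paired change from 0.47 SD to 0.64 SD, and the zero-event upper limit from 13.9% to 22.1%. Those sizes assume complete data for the half-widths, and exactly 12 or 20 vaccinated for the safety limits. The contradiction itself rests on no assumption. Which number is right cannot be settled from the document; only the sponsor can say. A planned sample size is a figure the trial relies on, so this must be corrected even though no analysis method changes.

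**What to change.** The sponsor should confirm the intended number and use it in sections 3.1, 4.2, 7.4 and 8.1.

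- If 20 is intended, change the number in sections 8.1 and 7.4.
- If 12 is intended, change section 3.1, including its split into two groups of about 10, and section 4.2.
- In either case, add a clause saying whether the number counts participants vaccinated or participants completing.

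Optionally, section 8.1 could carry one sentence on the resulting precision. At 20 with complete data this would be a half-width of about 0.47 SD for a paired change, and an upper limit of about 14% if none of the 20 has the event.

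The cost is a wording amendment to two sections plus one clause. No new procedure or analysis is needed.

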3.3.3 Safety Measure Outcomes

Classic metabolic, hematologic, and immune blood labs will be collected at Screening, Day 28, and Day 84 Visits and monitored for change following BCG vaccination. Four weeks after the first vaccination, we will assess the first vaccination site and evaluate for any signs of systemic infection prior to second BCG vaccination in the other arm. We will use the FDA Toxicity Grading Scale, as performed in vaccine trials, to denote changes from baseline.

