5.6 Termination of Study

This study may be prematurely terminated if, in the opinion of the investigator, there is sufficient reasonable cause.

Circumstances that may warrant termination include, but are not limited to:

1. Determination of unexpected, significant, or unacceptable risk to subjects;
2. Unsatisfactory enrollment;
3. Insufficient adherence to protocol requirements;
4. Data that are not sufficiently complete and/or evaluable;
5. If any grade 3 “severe” or higher adverse event occurs in three or more participants, or if participants have severe systemic reactions to the antigenicity of the vaccination with respiratory problems, the study protocol will be paused for review. The FDA, and all other relevant oversight bodies will be notified in a timely fashion if a batch of BCG is problematic. If during the study three or more subjects, representing greater than 25% of enrolled subjects, develop a systemic BCG infection in the absence of an underlying immunocompromised state, the study will be stopped for a study of this side effect.

If the study is prematurely terminated or suspended, the investigators will promptly inform the institution and regulatory authorities of the termination or suspension and the reason(s) for the termination or suspension. The IRB will also be informed promptly and provided the reason(s) for the termination or suspension by the investigator, as specified by applicable regulatory requirement(s).

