9 RISKS AND DISCOMFORTS

9.1 BCG Vaccine Risks

The BCG injection is associated with minimal, brief discomfort. The following risks may also be associated with BCG vaccination per the manufacturer product insert.

Although BCG vaccination often causes local reactions, serious or long-term complications are rare. Reactions that can be expected after vaccination include moderate axillary or cervical lymphadenopathy and induration and subsequent pustule formation at the injection site; these reactions can persist for as long as 3 months after vaccination. The intensity and duration of the local reaction depends on the depth of penetration of the puncture device and individual variations in patients' tissue reactions. Slight tenderness at the puncture site may be encountered as well as some itching. The initial skin lesions usually appear within 10–14 days and consist of small red papules at the site. The papules reach maximum diameter (about 3 mm) after 4 to 6 weeks, after which they may scale and then slowly subside. More serious local reactions include ulceration at the vaccination site, regional suppurative lymphadenitis with draining sinuses, and caseous lesions or purulent draining at the puncture site. These manifestations might occur up to 5 months after vaccination and could persist for several weeks.

Acute, localized irritative toxicities of BCG may be accompanied by systemic manifestations, consistent with a “flu-like” syndrome. Systemic adverse effects of 1–2 days’ duration such as fever, anorexia, myalgia, and neuralgia, often reflect hypersensitivity reactions. However, symptoms such as fever of 103 °F or greater, or acute localized inflammation persisting longer than 2–3 days suggest active infections, and evaluation for serious infectious complication should be considered.

Rare adverse events (mostly suppurative adenopathy) have been reported in Europe and other locales, mostly in the setting of mistakenly subcutaneous, rather than intradermal vaccination. The frequency of more severe cutaneous reactions, such as an ulcer >1 cm, axillary adenopathy which may be suppurative, or other localized skin reactions, is approximately 0.02% for first vaccinations and 0.04% for second vaccinations. Suppurative adenopathy is not treated but observed.

An allergic reaction can occur including serious reactions such as shock or anaphylaxis. Although anaphylaxis is very rare, the subjects will be observed for an allergic reaction after BCG vaccination.

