11.3.3 Assessment of Adverse Events

At each visit (including telephone visits), the subject will be asked if they had any problems or symptoms since their last visit in order to determine the occurrence of adverse events. If the subject reports an adverse event, the Investigator will probe further to determine:

- Type of event
- Date of onset and resolution (duration)
- Severity (mild, moderate, severe)
- Seriousness (does the event meet the above definition for an SAE)
- Causality, relation to investigational protocol
- Outcome

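### Cheap improvement: the only method section 8.1 names for safety change is a paired location test, insensitive to toxicity in a few subjects; add toxicity-grade shift tables and adverse event counts with exact intervals

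*Combined protocol and SAP*

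**What the plan says.** Section 3.2 makes the safety and tolerability of BCG vaccination the second of two secondary objectives. Section 3.3.3 has safety labs drawn at Screening, Day 28 and Day 84, and adds: "We will use the FDA Toxicity Grading Scale, as performed in vaccine trials, to denote changes from baseline".

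Section 8.1 is the whole statistical plan. On this point it plans to report "change in biomarkers, safety and clinical measures, with pre-post paired t-tests or non-parametric equivalents (Wilcoxon sign-rank) used to evaluate within subject change". It then states: "A P value <0.05 will be considered significant". It does not say whether tests are one- or two-sided. It declares all outcomes exploratory, with no claims attached and no sample size calculation. It mentions no toxicity grades, grade shifts, adverse event counts or intervals for event rates.

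The sample size is not consistent. Section 3.1 has twenty participants, about ten per cohort; sections 7.4 and 8.1 have twelve. Section 4.2 allows up to twenty-six to be screened and enrolled, with twenty expected to complete.

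**The concern.** Vaccine toxicity usually appears as a marked change in a few individuals while the rest stay near their starting values. A paired t-test asks whether the average change differs from zero, and each extreme value inflates the standard deviation along with the mean. The signed-rank test is not a test of means, but it is also a location test and gains little from a handful of extreme values. A lab with several subjects at a high grade could therefore be summarised as showing no significant change.

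Two gaps add to this. The grades that section 3.3.3 promises have no planned summary in section 8.1. Adverse event incidence has no pre-dose counterpart, so the one method named cannot summarise it. If no events of a given kind are seen, nothing in the plan says how high a true rate remains compatible with that result. At stake is how informative the report on secondary objective 2 will be for the placebo-controlled trials that section 8.1 says these data will inform.

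**Working it through.** The plan gives no power figure or test result for safety, so there is nothing of its own to reproduce.

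**Inputs.** Threshold P<0.05 and paired t or Wilcoxon (section 8.1); n=20 (section 3.1) or n=12 (section 8.1). Assumptions: a two-sided test, since sidedness is not stated; three affected subjects, all changing by the same amount L in the same direction on one lab. The change in the unaffected subjects is not given; it is set to zero first and then varied.

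**Step 1: paired t-test.** If k of n subjects change by L and the rest by zero, the mean change is kL/n and the variance is L²k(n−k)/(n(n−1)). L cancels:

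t = √(k(n−1)/(n−k)), with n−1 degrees of freedom.

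- n=20, k=3: t = √(3×19/17) = 1.831, two-sided P=0.083.
- n=12, k=3: t = √(3×11/9) = 1.915, two-sided P=0.082.
- n=20, k=4: t = √(4×19/16) = 2.179, P=0.042.

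This t is a maximum whenever the other subjects' changes sum to zero, because scatter among them, or unequal sizes among the three, adds variance without raising t. Changes in the ratio 3:4:5 give P=0.090 (n=20). If one of the three moves in the opposite direction, P=0.58.

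**Step 2: Wilcoxon, same data, other changes exactly zero.** Exact with zeros dropped, P=0.25; normal approximation, 0.109; Pratt's handling of zeros, 0.084. The exact version with zeros dropped needs six non-zero changes to pass 0.05 (P=0.031).

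**Step 3: how far this depends on the assumptions (n=20, k=3).**

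| Variation | Result |
|---|---|
| One-sided t-test | P=0.041 |
| Other 17 each shift by 3% of L | t-test P=0.040, two-sided |
| Other 17 each shift by 5% of L | t-test P=0.023, two-sided |
| Other 17 random, mean 0, SD 1; L = 3, 5, 10 SD | t-test P<0.05 in 18%, 20%, 14% of 40,000 simulated trials; Wilcoxon about 13% |
| As above, mean 0.3 SD | t-test 62%, 65%, 56%; Wilcoxon about 53% |
| Mean 0, L = 50 SD | t-test about 0% |

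So significance depends largely on small movements in the unaffected subjects. With no expected shift in them, a very large change in the affected three makes the t-test less likely to reach P<0.05.

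**Step 4: what counts would show.** Three affected subjects give 3/20 = 15% (exact 95% CI 3.2% to 37.9%) or 3/12 = 25% (5.5% to 57.2%). An exact McNemar test of three shifts against none gives P=0.25, so another P value is not the remedy.

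**Step 5: zero events.** The exact two-sided 95% upper limit is 1 − 0.025^(1/n): 16.8% for n=20, 26.5% for n=12, 30.8% for a cohort of 10. Zero is the likely result for rare events: section 9.1 puts more severe skin reactions at "approximately 0.02% for first vaccinations and 0.04% for second vaccinations", so 20 subjects given two doses would be expected to yield 20 × (0.0002 + 0.0004) = 0.012.

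**The case against.** The best defence is that the paired tests are not the whole safety assessment. Section 8.1 says safety change will be described, and section 3.3.3 grades it. Section 11.3 has every adverse event recorded, and clinically significant lab abnormalities count as adverse events. All outcomes are exploratory, so no conclusion of no harm formally rests on P>0.05. Paired tests are also a reasonable exploratory look at continuous labs such as CRP and ESR after a live vaccine. Much of this stands: it makes the point smaller and argues against deleting the tests. But describing change commits to no grade table, listing or interval. Under section 11.3.1 a lab abnormality becomes an adverse event only if a clinician investigator judges it clinically significant, so a graded change not so judged has only the section 8.1 analysis as its planned route into the results.

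Three stronger readings are tempting and not supported.

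- *That the tests cannot reach P<0.05 with three of 20 severely affected.* They can, if the test is one-sided, if the others shift slightly, or by chance (Step 3).
- *That a non-significant test would hide or disable the pause in section 5.6.* The pause applies when any grade 3 "or higher adverse event occurs in three or more participants". It is a count that needs no P value, and the events need not be the same abnormality or a lab finding at all.
- *That grade 3 events cannot be counted because section 11.3.3 records severity only as mild, moderate or severe.* Section 5.6 itself labels grade 3 as severe, so the count can be made from the log; life-threatening events are also captured separately as serious adverse events (section 11.3.1.1).

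**Conclusion.** The point holds as a modest improvement to the analysis plan, not as a flaw that endangers subjects or invalidates the trial. Section 8.1 names one method for safety change, and it is insensitive to toxicity in a few people: three of 20 equal changes give at best two-sided P=0.083 by t-test, and 0.084 to 0.25 by Wilcoxon. The t-test figure assumes a two-sided test, the same measure and direction, and realised changes in the other 17 that sum to zero; the Wilcoxon range assumes those changes are exactly zero. Using n=12 barely alters these P values.

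The omission of any grade summary, adverse event count or interval from section 8.1 does not depend on those assumptions. The sample size conflict matters more for the intervals: the limit for zero events is 16.8% or 26.5% according to which number is right.

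**What to change.** In section 8.1, keep the paired tests only as a supplementary exploratory look at continuous labs, and make the main safety summary:

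1. For each lab that the FDA scale covers, a shift table from Screening grade to worst post-dose grade, listing every subject who reaches grade 3 or above. The scale is not reproduced in the document, so whether it covers every safety lab, including CRP and ESR, should be checked when the table is specified.
2. For each adverse event, the number and percentage of vaccinated subjects affected, with exact (Clopper-Pearson) 95% confidence intervals.
3. A sentence stating that zero events excludes only rates above 16.8% (n=20) or 26.5% (n=12).

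Reconcile the twenty in section 3.1 with the twelve in sections 7.4 and 8.1 so that the right limit is quoted, and recalculate it if the number actually vaccinated differs.

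The cost is a few sentences and a little more tabulation, with no new visits or samples. The safety statement will look less favourable because its upper limits are shown.

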3.3 Study Outcome Measures

3.3.1 **CSF and Blood Biomarker Outcomes**

CSF and blood will be collected at Baseline, Day 28 (blood only) and Day 84 Visits to examine biochemical biomarkers of:

1. Target engagement: BCG, purified protein derivative (PPD) and / or mycobacterium tuberculosis (heat-killed, mTB) – induced cytokine response in peripheral blood cells will be used to evaluate for BCG vaccine-induced immunity.
2. Pharmacodynamic response: a) Circulating cytokines and other related blood- and CSF-based IIR biomarkers relating to innate and adaptive immune responses; b) Epigenetic changes in peripheral blood cells and / or CSF- derived cell populations as indicators that BCG can lead to long term changes in peripheral and central nervous system immune cells.
3. AD pathophysiology: Amyloid- β 42/40, phospho-tau, total tau and / or neurofilament light protein biomarkers (ATN) and other exploratory AD-relevant synaptic and IIR biomarkers may be compared within subjects over time and between subjects and groups.
4. BCG effects on the interactions of IIR and amyloid: We will perform PBMC stimulation with A β 42 and positive-control antigens (e.g. lipopolysaccharide) and measure the molecular response in the supernatant at multiple timepoints after BCG /treatment. A β 42 has immunostimulatory / inflammatory effects that increase with AD progression and may be modulated by an immune-provoking stimulus such as BCG.
5. Additional related Alzheimer's Disease and immune measures in plasma, CSF, and their cell populations at the transcriptional, protein, or epigenetic levels.

We have several robust platforms in the [name] lab (which serves as the Biomarker Core of the Massachusetts Alzheimer's Disease Research Center) to conduct these assays, including highly validated Euroimmun assays, Fujirebio Lumipulse assays, Meso Scale Discovery with plates run on a new Tecan EV0200 multi-functional robotic liquid handling platform, and Quanterix SR-X for ultrasensitive Simoa assays. We have exhaustively validated many assays specifically for use in short-term clinical trials⁴⁹, and all assays that we propose demonstrate good precision and biotemporal stability. Change in a composite score from Baseline will be used as an outcome of response to BCG.

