6 STUDY PROCEDURES

6.1 Schedule of Events

Activity	Phone Screen	Screening Visit	Baseline Visit/ BCG Vaccine 1	BCG Vaccine 2	Outcome Visit/ Early Termination	Check-In Phone
		<-28days	Day 1	Day 28 +14 days	Day 84 ±5 days	Day 98 ±5 days
Informed Consent		x				
Inclusion/Exclusion Review	x	x				
Demographics	x	x				
Create IBCID		x				
Medical History	x	x				
Concomitant Medication Review	x	x	x	x	x	x
Family History		x				
Vital Signs, Height, Weight ¹		x	x	x	x	
Physical & Neurological Exam		x				
Screening Lab Tests for Eligibility ²		x				
BCG Vaccination			x	x		
Vaccination Site Monitoring			x	x	x	
Fundoscopy					x	
Safety Lab Tests ³				x	x	
Blood Draw for Biomarkers ⁴			x	x	x	
COVID-19 Testing ⁵		x				
PT/INR		x			x	
Fasting Lumbar Puncture for Biomarkers ⁴			x		x	
MoCA and FAQ		x			x	
Cognitive/Behavioral Assessment ⁶			x		x	
Adverse Event Review		x	x	x	x	x

[1] Height and weight will be measured and recorded at the Screening visit only.

[2] Eligibility lab tests include CBC with diff, CMP, TSH, Folate, B12, HIV antibodies, serum immunoglobulins, ESR, CRP, QuantiFERON-TB Gold Test, urinalysis

[3] Safety lab tests include CBC with diff, CMP, CRP and ESR.

[4] Blood biomarkers will include PBMCs for PPD and amyloid-beta stimulation assay / flow cytometry, and serum for IIR and AD biomarkers. CSF biomarkers will be used for cytology, IIR and AD biomarkers tubes for monocyte levels of innate immunity.

[5] COVID-19 Testing includes SARS-CoV-2 PCR (nasal swab)

[6] Cognitive assessments will include RBANS, NPI-Q

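### The pre-post paired tests in section 8.1 leave the post visit, cohort, Day 28 blood and early termination values unspecified, so the Day 84 change may be diluted across cohorts or understated when participants leave

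*Combined protocol and SAP*

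**What the plan says.** Section 8.1 evaluates change "with pre-post paired t-tests or non-parametric equivalents (Wilcoxon sign-rank) used to evaluate within subject change". No other inferential method is given. The section describes a single sample and states that "A P value <0.05 will be considered significant". It also says that "All outcomes in this pilot study are considered exploratory and no claims are attached to them" and that "No sample size calculations are performed as no prespecified comparisons are planned".

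The design collects more than a two-point comparison needs. Section 3.1 plans "Twenty participants (approx. n=10 cognitively normal, n=10 mild cognitive impairment"). Section 3.3.1 has biomarker blood drawn at Baseline, Day 28 and Day 84, and CSF at Baseline and Day 84 only. For the AD pathophysiology markers, it adds that they "may be compared within subjects over time and between subjects and groups", without a method.

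The schedule in section 6.1 has one column, headed "Outcome Visit/ Early Termination", with the Day 84 ±5 window. Sections 5.5 and 6.2.6 offer an early termination visit, with biomarker blood, to anyone who withdraws after the first vaccination. The participant may decline any part of it.

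**The concern.** A paired test uses only participants with both values, and it has no cohort term. Section 8.1 leaves four things open:

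- which visit is the post visit for each outcome;
- whether the two cohorts are analysed together or separately;
- what happens to a participant who has Day 28 blood but no Day 84 blood;
- whether an early termination value, taken on whatever day the participant leaves, can stand as the Day 84 value.

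The primary objective in section 3.2 is to pick the most promising biomarkers, partly by their response to BCG, and section 8.1 says the findings will inform later placebo-controlled trials. A diluted or understated change therefore bears on which markers are carried forward.

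**Working it through.** **Inputs.** The plan gives no power, effect size, SD, correlation or post-vaccination dropout rate, so there is no figure of its own to reproduce. From the documents: 20 participants, about 10 + 10 (section 3.1); threshold 0.05 (section 8.1, taken as two-sided). Everything else below is assumed. Changes are in units of the SD of change.

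**1. Cohort dilution.** Cohort changes 0 and +0.8 SD, 10 each, SD 1 within cohort.
- Pooled mean change = (0 + 0.8)/2 = 0.40.
- Spread of the pooled changes = √(1 + 0.4² × 20/19) = 1.08, so the expected t is roughly 0.40 × √20 / 1.08 = 1.66.
- Responding cohort alone: 0.8 × √10 = 2.53.

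Share of simulated trials with P below 0.05:

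| Cohort changes (SD) | Pooled test | +0.8 SD cohort alone | Cohort difference |
|---|---|---|---|
| +0.8 / +0.8 | 92% | 62% | 5% |
| +0.4 / +0.8 | 70–71% | 62% | 14% |
| 0 / +0.8 | 34% | 62% | 39–40% |
| −0.4 / +0.8 | 8% | 62% | 72% |

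Pooling is the better test when the cohorts respond alike. It loses when one does not respond.

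**2. Participants without a Day 84 value.** n = 20; true mean changes 0.4 SD (Day 28) and 0.8 SD (Day 84); correlation between the two changes 0.5 or 0.7. Leavers are those with the highest Day 28 change plus noise of SD 0.5.
- Completer estimate: mean Day 84 change among those who stay.
- Likelihood estimate using Day 28: completers' Day 84 mean + b × (Day 28 mean of all − Day 28 mean of completers), where b is the completers' slope of Day 84 change on Day 28 change.

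| Lost of 20 | Completers, correlation 0.5 / 0.7 | Likelihood |
|---|---|---|
| 1 | 0.76 / 0.74 | 0.80 |
| 2 | 0.72 / 0.69 | 0.80 |
| 4 | 0.65 / 0.59 | 0.80 |

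Limits of this correction:
- If leaving is random, completers are essentially unbiased.
- If leaving tracks the Day 84 response and four are lost, completers give about 0.5 and the likelihood estimate 0.56–0.62, so the correction is only partial.
- A model with only a random intercept gives about 0.77 and 0.71 with four lost on Day 28 response (baseline SD 1, independent of change). The covariance structure matters.
- Someone who leaves before Day 28 has no Day 28 value to use.

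**3. Early termination value used as Day 84.** If four of 20 leave at random and their early values average 0.2 SD, the mean is (16 × 0.80 + 4 × 0.20)/20 = 0.68 against a true 0.80. The direction is not fixed. With true changes of 0.5 SD at both visits, correlation 0.3 to 0.7, and the two or four participants with the largest Day 28 change lost, substituting their Day 28 values gives a bias of +0.05 to +0.18 SD. Dropping them gives −0.05 to −0.23 SD. The plan does not say which applies.

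**4. Precision by cohort.** 95% half-widths:
- 10 per cohort: 2.262/√10 = 0.72 SD within a cohort; 2.101 × √(2/10) = 0.94 SD for the difference.
- 6 per cohort (an assumed even split of the 12 in section 8.1): 2.571/√6 = 1.05 SD; 2.228 × √(2/6) = 1.29 SD.

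**The case against.** The plan can be defended on several grounds, and much of the defence stands.

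- **Silence is not a decision.** A reader might infer that the plan pools the cohorts and ignores Day 28. It does not say so. Pre-post can cover Baseline to Day 28, and nothing bars running the tests by cohort. The supported statement is that these choices are not specified.
- **No promise is broken.** A reader might take section 3.3.1 as a commitment to compare groups. Its wording is optional ("may be compared within subjects over time and between subjects and groups") and applies to the AD markers.
- **The shared column is a procedure list.** Sections 6.2.4 and 6.2.6 define the Outcome and Early Termination visits separately, and the data system in section 12.3 can flag values out of window. No analysis rule keeps early values out of Day 84, but none puts them in. Dropping a leaver and using the early value are alternatives for the same person and marker, not two errors together.
- **Heavy selective dropout is assumed.** Section 4.2 expects twenty completers, and under section 5.4.2 participants whose second dose is withheld may stay in the study. Nothing indicates that four of 20 leave or that strong responders leave.
- **Opposite cohort responses are assumed too.** The 8% against 72% contrast needs them, and no document suggests them. At 0 and +0.8 SD the pooled test and the cohort difference are close, 34% and about 40%.
- **Day 28 helps only blood markers.** CSF and the four clinical scales have two visits.

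Exploratory status limits the consequence and explains the lack of multiplicity correction. It does not define the change being estimated, and section 8.1 still attaches a significance threshold to it.

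**Conclusion.** The concern holds in a limited form. Section 8.1 names paired tests only and leaves the post visit, cohort, Day 28 blood and early termination values without a rule, while the trial collects data that a better-specified analysis could use. With complete data and similar cohorts the paired test is adequate.

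The plausible losses are moderate: dilution if only one cohort responds, and understatement of a 0.80 SD change by about 0.04 to 0.11 SD with one or two of 20 lost on Day 28 response. With four lost it is 0.15 to 0.21 SD, but that is a strong assumption. A reader might conclude that the planned result will be biased, or that a model using Day 28 would recover the right answer. The documents support neither: random leaving gives no bias, and the model corrects only part of it if leaving depends on the Day 84 response. Because the remedy costs almost nothing, the change should be made.

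**What to change.** Rewrite the methods paragraph in section 8.1.

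1. **Blood markers:** fit one repeated-measures model to all available values, with visit (Baseline, Day 28, Day 84), cohort and cohort × visit, and an unstructured within-participant covariance, not only a random intercept. Report Day 28 and Day 84 change with 95% CI by cohort, and the cohort difference, as exploratory estimates.
2. **Two-visit outcomes (CSF, RBANS, NPI-Q, MoCA, FAQ):** name the pre and post visits (MoCA and FAQ start at Screening). Report paired change by cohort with 95% CI and the number of complete pairs. No Day 28 correction is possible here.
3. **Early termination values:** record them at their actual study day and count them as Day 84 only if taken within Day 79–89.
4. **Paired tests:** keep them as a check.
5. **Sample size:** section 8.1 says "twelve older adult volunteers with normal cognition or MCI will be recruited" and section 7.4 also refers to 12 participants, whereas sections 3.1 and 4.2 give twenty. These must be reconciled. The intervals are wide at 20 and wider at 12.

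Cost: about one paragraph of text. No new visits, samples or participants.
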